22. Has known psychiatric or substance abuse disorders that would interfere with the participant's ability to cooperate with the requirements of the study.
23. Is pregnant, breastfeeding, or expecting to conceive or father children within the projected duration of the study, starting with the Screening Visit through 120 days after the last dose of study intervention.
24. Has not fully recovered from any effects of major surgery without significant detectable infection. Surgeries that required general anesthesia must be completed at least 2 weeks before first study intervention administration. Surgery requiring regional/epidural anesthesia must be completed at least 72 hours before first study intervention administration and participants should be recovered.
25. Has a tumor(s) in direct contact or encases a major blood vessel with or without ulceration and/or fungation onto the skin surface at the projected injection site in the head or neck.
26. Has a history of reirradiation for HNSCC at the projected injection site in the head and neck.

Prior/Concomitant Therapy

27. Has received a live-virus vaccine within 30 days of planned treatment start. Seasonal flu vaccines that do not contain live virus are permitted.
28. Drug-drug interactions have to be taken into consideration, and decisions whether a particular drug can be used as a concomitant medication in the study should be based on recommendations at the time of the study and depending on the mechanism of action of the study intervention. Participants on ART agents with a potentially significant overlapping toxicity profile should be excluded if the therapy cannot be switched to the regimen without overlapping toxicity.
29. Has been treated with a STING agonist (eg, MK-1454, ADU-S100).

Prior/Concurrent Clinical Study Experience

30. Is currently participating and receiving study therapy or has participated in a study of an investigational agent and received study therapy, or used an investigational device, any of which occurred within 4 weeks of the first dose of treatment. Note: Participation in the Follow-up Phase (receiving no study treatment) of a prior study is allowed.

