6.2 Preparation/Handling/Storage/Accountability

6.2.1 Dose Preparation

MK-1454 will be administered as a sterile aqueous solution with a total volume of injectate of up to 3 mL per treatment visit for all injected lesions combined. MK-1454 will be administered by injection into cutaneous, subcutaneous, and/or nodal lesions that are visible, palpable, and/or detectable by ultrasound guidance or cross-sectional imaging guidance as clinically appropriate.

Each participant randomized to Arm 1 will receive a CCI dose of MK-1454 diluted in a volume of 1.0 mL to 3 mL of injectate. The volume of injectate delivered to each lesion will be based on the longest dimension of the lesion(s) intended for injection as shown in [Table 3](#), and on the total number of lesions injected at the treatment visit. Injection of more than 1 lesion, if feasible, is suggested.

Regarding prioritization of lesions to be injected at a treatment visit, any new or progressing lesion should be prioritized first for injection, followed by injection of the largest lesion, with up to a total volume of injectate of 3 mL per treatment visit (Appendix 8).

A maximum of 3 lesions may be injected per treatment visit, with a minimum injectate volume of 1.0 mL ([Table 4](#)). The maximum total injectate volume per treatment visit per participant is 3 mL for all participants. Documentation of dose volume administered per lesion will be recorded. For image-guided procedures, document the needle tip within the lesion during IT injection. Detailed guidance on injectate volume and lesion injection is provided in the Procedures Manual.

For lesions that are no longer visible following treatment, discuss with Sponsor for continued injection. Distant lesion(s) assessed for "abscopal" response should not be injected, unless approved by the Sponsor Medical Monitor or designee. Deviation from the injectate volumes specified in [Table 3](#) and [Table 4](#) for individual lesions may be permitted upon approval by the Sponsor Medical Monitor or designee.

Table 3 Determination of Intratumoral MK-1454 Injection Volume Per Lesion Based on Lesion Size

Lesion Size (longest dimension)	Injection Volume
>5 cm	3 mL
>2.5 cm to 5 cm	2 mL
≥1.0 cm to 2.5 cm	1 mL

Table 4 Determination of Intratumoral MK-1454 Total Injectate Volume Based on Number of Lesions Injected Per Treatment Visit

Deliverable Volume		1 mL	2 mL	3 mL
Number of Lesions	1	1 × 1 mL	1 × 2 mL	1 × 3 mL
	2	NA	2 × 1 mL	1 × 1 mL + 1 × 2 mL

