6.6.1.1 Dose Modification for MK-1454

Guidelines for dose modification and/or treatment discontinuation for drug-related injection site reactions and for CRS AEs are provided in [Table 5](#) and [Table 6](#), respectively.

The investigator should first assess an AE to determine the CTCAE Version 5.0 severity grade. For AEs that are \leq Grade 2, the decision to hold treatment is per medical assessment by the investigator. Once the AE has resolved to Grade 0 or 1, treatment with MK-1454 can be restarted. If the AE persists, discuss with the Sponsor with regard to selecting a different injection site or discontinuation. MK-1454 should be discontinued permanently following a severe or life-threatening AE.

In case toxicity does not resolve to Grade 0-1 within 12 weeks after last intervention, MK-1454 should be discontinued after consultation with the Sponsor.

With investigator and Sponsor agreement, participants with a laboratory AE still at Grade 2 after 12 weeks may continue intervention in the study only if asymptomatic and controlled.

After any Grade 4 drug-related AE, participants should not restart study intervention without consultation with the Sponsor (Toxicity must have resolved to Grade 0-1 or baseline prior to restarting).

Pembrolizumab treatment will be modified for the AEs described in Section 6.6.1.4.

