6.6.1.1.1 Guidelines for Management of Intratumoral Injection Site Reactions

Guidelines for management of injection site reaction from intratumoral injection of MK-1454 are detailed in [Table 5](#).

Table 5 Intratumoral Injection Site Reaction Management Guidelines

NCI CTCAE Grade	MK-1454 Dose Modification	Treatment
Grade 1 Tenderness with or without associated symptoms (eg, warmth, erythema, itching)	No dose reduction warranted.	Observe. Dose to be held per medical assessment of the investigator. Analgesia as needed.
Grade 2 Pain; lipodystrophy; edema; phlebitis	Per medical assessment of the investigator: 
 Consider holding dose until resolution to Grade 1 or baseline. Consider decreasing dose of IT MK-1454 to [REDACTED] and limit injections to a maximum of 2 lesions per study visit. If AE persists, discuss continuation with Sponsor. 	Observe. Local care to injection site. Analgesia as needed. Consider injection into a different lesion, if available.
Grade 3 Ulceration or necrosis; severe tissue damage; operative intervention indicated	
 Hold dose until resolution to Grade 1 or Baseline. Decrease dose of IT MK-1454 to [REDACTED] and limit injections to a maximum of 2 lesions per study visit. If AE persists, discuss continuation with Sponsor. 	Wound care with consultation from institutional wound care specialist. Analgesia as needed. Consider injection into a different lesion, if available.
Grade 4 Life-threatening consequences; urgent intervention indicated	
 Permanently discontinue IT MK-1454 treatment. 	Aggressive wound care with surgical consultation. Analgesia as needed.

AE adverse events; CTCAE Common Terminology Criteria for Adverse Events (Version 5.0); IT intratumoral; NCI National Cancer Institute.

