10.10 Appendix 10: itRECIST Supplementary Figures

[figure not shown]
Figure 5 Algorithm for Classification of Lesions at Baseline

Source: Adapted from [Goldmacher, G. V., et al 2020].

Lesions are classified first as measurable or nonmeasurable using the standard RECIST 1.1 rules for measurability. Measurable lesions (those eligible for selection as target lesions) are then classified as target (selected to be followed quantitatively) or nontarget (selected to be followed qualitatively), and the decisions about which lesions are to be injected are made based on the prioritization rules discussed. Lesions selected for injection may be either target or nontarget in RECIST 1.1 terms. Between 1 and 5 lesions should be classified as target injected, and between 1 and 5 should be classified as target noninjected, for a maximum of 10 target lesions. All lesions not chosen as target are followed qualitatively as nontarget, and some of these may be selected for injection at baseline. T-I lesions and T-NI lesions each have their own distinct SOD. A combined SOD also includes all target lesions, injected and noninjected. NT-I and NT-NI lesions are followed qualitatively, exactly as in RECIST 1.1, classified in aggregate as showing complete response, unequivocal progression, or neither (called non-CR/non-PD in RECIST 1.1).

[figure not shown]
Figure 6 Reclassification of Noninjected Lesions

Source: Adapted from [Goldmacher, G. V., et al 2020].

Target or nontarget noninjected lesions can be reclassified as injected lesions if the decision is made to inject them after baseline assessment. Nontarget noninjected lesions may be injected if previously injected nontarget lesions regress completely or become inaccessible or if a patient factor such as injection site reaction or patient intolerance precludes further injection. Lesions initially selected as target noninjected should remain noninjected for as long as possible so the maximal noninjected effect can be evaluated, but they may be injected if they are enlarging, or if no other lesions are available for injection, especially if the lesions initially designated as target noninjected are not regressing. The barrier between target and nontarget categories means that all lesions remain target and nontarget in accordance with the initial designation, regardless of whether they are subsequently injected.

[figure not shown]
Figure 7 Overall Response Assessment Until Disease Progression

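### Head or neck lesions first chosen for injection on study carry no re-irradiation condition in the supplied text, and the major-vessel bar continues only as Appendix 8 guidance that does not explicitly cover direct contact without encasement

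*Combined protocol and SAP*

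**What the plan says.** **At entry.** Section 5.2 has two exclusions tied to a location in the head or neck. Criterion 26 excludes a participant who "Has a history of reirradiation for HNSCC at the projected injection site in the head and neck". Criterion 25 excludes tumor "in direct contact or encases a major blood vessel with or without ulceration and/or fungation onto the skin surface at the projected injection site". Both are absolute.

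**During treatment.** Three places let the injected lesion change:

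- Section 6.2.1: "any new or progressing lesion should be prioritized first for injection, followed by injection of the largest lesion".
- Table 5 (Section 6.6.1.1.1), after a Grade 2 or Grade 3 injection site reaction: "Consider injection into a different lesion, if available".
- Appendix 10, on target lesions not injected at baseline: "they may be injected if they are enlarging, or if no other lesions are available for injection".

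**Limits on changing lesion.** Section 6.2.1 says that distant lesions followed for an abscopal "response should not be injected, unless approved by the Sponsor Medical Monitor or designee". Section 6.6.1.1 says: "If the AE persists, discuss with the Sponsor with regard to selecting a different injection site or discontinuation". Appendix 10 also says: "Lesions initially selected as target noninjected should remain noninjected for as long as possible".

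**Safety guidance.** Section 6.2.1 refers to Appendix 8 for prioritizing lesions. Appendix 8 applies at each treatment visit and ranks patient safety first. It names vessels within and next to a lesion as important factors, prefers that adjacent vessels not be crossed, and advises against areas of encasement in high-risk locations, with the carotid artery as its head and neck example. It describes itself as guiding principles and leaves the final choice to clinical judgment and patient tolerance.

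**The concern.** The two entry criteria mark kinds of site that the sponsor judged too hazardous to inject. The hazard belongs to the site, but the rule attaches to the site foreseen at entry. However broadly the projected site is read, it cannot include a lesion that appears after entry. On a narrower reading it also omits baseline lesions that were not meant to be injected and are picked up later because they enlarge.

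A participant with a re-irradiated or vessel-abutting lesion elsewhere in the head or neck can therefore enroll. If that lesion progresses, the prioritization rule moves it up the injection list. Section 4.2 gives bleeding and infection among its reasons for not injecting placebo into lesions in Arm 2, so the protocol itself treats injection as a procedure with real risk. Only Arm 1 is exposed to it.

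**Working it through.** The point is textual. It rests on no sample size, power, alpha or event figure, so there is no plan figure to reproduce. The check is whether each entry condition reappears wherever a lesion can be chosen for injection after entry.

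| Place | Re-irradiated site | Encases a major vessel | Touches a major vessel, no encasement |
|---|---|---|---|
| 5.2, criteria 25 and 26 (entry, projected site) | Barred | Barred | Barred |
| 6.2.1, new or progressing lesions first | Not mentioned | Only through its reference to Appendix 8 | Only through its reference to Appendix 8 |
| Table 5, different lesion after a reaction | Not mentioned | Not mentioned | Not mentioned |
| Appendix 10, noninjected lesion becomes injected | Not mentioned | Not mentioned | Not mentioned |
| Appendix 8, Patient Safety | Not mentioned | Advised against | Adjacent vessels are a safety factor, ideally not crossed; no explicit bar |

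**Re-irradiation.** The other radiation text was read for anything that might fill the first column.

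- Section 5.1, criterion 3, concerns whether a lesion in an irradiated area counts as measurable. It does not say whether the lesion may be injected, though it shows that irradiated fields are expected in this population.
- Section 5.2, criterion 4, is a two-week washout with recovery from earlier treatment.
- Sections 6.5.2 and 6.5.3 concern radiotherapy given during the study.

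None limits the choice of a later injection site. Criterion 26 has no on-study counterpart in the supplied text.

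**Vessels.** Encasement moves from an absolute exclusion to advice. For contact without encasement, the nearest wording is the preference not to cross adjacent vessels. That governs the needle path, not whether the lesion may be injected at all.

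**Limits on lesion changes.** Sponsor approval for abscopal lesions, Sponsor discussion of a persisting adverse event, and the instruction to leave target noninjected lesions alone as long as possible all reduce how often a new lesion is chosen. None states a condition on re-irradiation or vessel contact.

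**Number exposed.** About 200 participants are randomized 1:1 (Section 4.1), so 200 × 1/2 = 100 are assigned to injections. The documents give no frequency of re-irradiation, vessel contact or change of injected lesion, so the affected share of those 100 cannot be calculated.

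**The case against.** The strongest reply is that the vessel half is largely handled. Section 6.2.1 cites Appendix 8 in the very sentence that ranks new and progressing lesions first, and Section 8.1.8 cites it again. Appendix 8 repeats that safety and accessibility stay primary for new or enlarging lesions. Section 7.1 requires stopping treatment that places a participant at unnecessary risk. This stands as far as it goes: vessel proximity is not ignored. What remains is the step from an absolute bar to judgment, and the lack of an explicit rule on contact without encasement. None of this text supplies a re-irradiation condition.

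A second reply is that the Procedures Manual, cited in 6.2.1 and Appendix 8 for detailed injection guidance, may already contain the rule. That is possible and cannot be checked here.

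A third is that the situation is uncommon. Injecting a truly new lesion mostly means treating beyond first progression, which under Section 8.2.5 requires clinical stability and further consent. That is fair, although an enlarging lesion or a switch after an injection site reaction need not involve progression.

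Three stronger readings should be resisted.

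- **On-study radiotherapy readily creates re-irradiated sites.** Section 6.5.3 alone might suggest so. Section 6.5.2, however, prohibits radiation during treatment apart from exceptional cases (a symptomatic solitary lesion, or the brain) after Sponsor consultation, and 6.5.3 requires continuation to be discussed with the Sponsor. The route is remote.
- **An early vessel check is impossible before the first on-study scan.** Sections 5.1 and 6.2.1 and Appendix 8 provide for ultrasound or, for some lesions, cross-sectional guidance at injection. It is not required for every lesion, but current imaging will exist for some.
- **Lesions cleared at entry need re-checking at every scan.** The gap concerns lesions first chosen on study, and the comparison above does not support going further.

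**Conclusion.** The point holds for the supplied text. Re-irradiation is a complete gap for head or neck lesions first selected on study. For major vessels the loss is partial: encasement is covered by advice instead of a bar, and direct contact without encasement is left to clinical judgment.

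This is a participant-safety matter in Arm 1, where about 100 people are to be injected. The number affected is unknown and may be small. No statistical quantity in the plan changes.

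A reader might infer that the protocol directs sites to inject hazardous lesions, or that vessel risk is disregarded after entry. The documents support neither inference, because Appendix 8 puts safety ahead of lesion priority and Sponsor involvement limits some changes. The conclusion assumes that the Procedures Manual and the redacted text contain no equivalent rule. If they do, only a cross-reference is missing. Given the low cost, this is a change worth making, though not a reason to doubt the trial.

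**What to change.** Add one or two sentences to Section 6.2.1 and to the Patient Safety step of Appendix 8. They should say that any head or neck lesion newly selected for injection on study must meet the conditions of criteria 25 and 26: not at a re-irradiated site, and neither in direct contact with nor encasing a major blood vessel. Compliance should be judged from treatment history and the most recent available imaging, including any ultrasound or cross-sectional guidance used for the injection itself. No extra scans are needed. If the Procedures Manual already contains this rule, cite it in both places.

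The cost is a short text change, with no added imaging or visits. The downside is that a few Arm 1 participants may have fewer lesions available for injection, a restriction of the kind that the protocol already imposes at entry.

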5.3 Lifestyle Considerations

5.3.1 Meals and Dietary Restrictions

Participants should maintain a normal diet unless modifications are required to manage AEs such as diarrhea, nausea or vomiting.

5.4 Screen Failures

Screen failures are defined as participants who consent to participate in the clinical study, but are not subsequently enrolled in the study. A minimal set of screen failure information is required to ensure transparent reporting of screen failure participants to meet the CONSORT publishing requirements and to respond to queries from regulatory authorities. Minimal information includes demography, screen failure details, eligibility criteria, and any AEs or SAEs meeting reporting requirements as outlined in the data entry guidelines.

Subjects may be rescreened after initially failing to meet the inclusion/exclusion criteria. Results from assessments performed during the initial screening period are acceptable in lieu of a repeat screening test if performed within the specified time frame and the inclusion/exclusion criteria are met. Subjects may be rescreened more than once at the discretion of the investigator.

5.5 Participant Replacement Strategy

A participant who withdraws from the study will not be replaced.

6 STUDY INTERVENTION

Study intervention is defined as any investigational intervention(s), marketed product(s), placebo, or medical device(s) intended to be administered to a study participant according to the study protocol.

Clinical supplies (study interventions provided by the Sponsor) will be packaged to support enrollment as required. Clinical supplies will be affixed with a clinical label in accordance with regulatory requirements.

6.1 Study Intervention(s) Administered

The study intervention(s) to be used in this study are outlined in [Table 2](#).

Table 2 Study Interventions

Arm Name	Arm Type	Intervention Name	Type	Dose Formulation	Unit Dose Strength(s)	Dosage Level(s)	Route of Administration	Regimen/ Treatment Period/ Vaccination Regimen	Use	IMP/ NIMP	Sourcing
Arm 1	Experimental	Pembrolizumab	Drug	Solution for Infusion	100 mg /4 mL	200 mg	IV Infusion	200 mg IV Q3W	Experimental	IMP	Sponsor
Arm 1	Experimental	MK-1454	Drug	Sterile Solution	CCI mg/mL	CCI	Intratumoral	CCI IT Q1W × 6, then Q3W	Experimental	IMP	Sponsor
Arm 2	Active Comparator	Pembrolizumab	Drug	Solution for Infusion	100 mg /4 mL	200 mg	IV Infusion	200 mg IV Q3W	Experimental	IMP	Sponsor

IMP Investigational Medicinal Product; IV intravenous; NIMP Noninvestigational Medicinal Product; Q1W once each week; Q3W every 3 weeks.
 Definition of IMP and NIMP is based on guidance issued by the European Commission. Regional and/or Country differences of the definition of IMP/NIMP may exist. In these circumstances, local legislation is followed.

All supplies indicated in [Table 2](#) will be provided per the "Sourcing" column depending upon local country operational requirements. If local sourcing, every attempt should be made to source these supplies from a single lot/batch number where possible (eg, not applicable in the case where multiple lots or batches may be required due to the length of the study, etc.).

1. Refer to Section 8.1.8 for details regarding administration of the study intervention.

6.2 Preparation/Handling/Storage/Accountability

6.2.1 Dose Preparation

MK-1454 will be administered as a sterile aqueous solution with a total volume of injectate of up to 3 mL per treatment visit for all injected lesions combined. MK-1454 will be administered by injection into cutaneous, subcutaneous, and/or nodal lesions that are visible, palpable, and/or detectable by ultrasound guidance or cross-sectional imaging guidance as clinically appropriate.

Each participant randomized to Arm 1 will receive a CCI dose of MK-1454 diluted in a volume of 1.0 mL to 3 mL of injectate. The volume of injectate delivered to each lesion will be based on the longest dimension of the lesion(s) intended for injection as shown in [Table 3](#), and on the total number of lesions injected at the treatment visit. Injection of more than 1 lesion, if feasible, is suggested.

Regarding prioritization of lesions to be injected at a treatment visit, any new or progressing lesion should be prioritized first for injection, followed by injection of the largest lesion, with up to a total volume of injectate of 3 mL per treatment visit (Appendix 8).

A maximum of 3 lesions may be injected per treatment visit, with a minimum injectate volume of 1.0 mL ([Table 4](#)). The maximum total injectate volume per treatment visit per participant is 3 mL for all participants. Documentation of dose volume administered per lesion will be recorded. For image-guided procedures, document the needle tip within the lesion during IT injection. Detailed guidance on injectate volume and lesion injection is provided in the Procedures Manual.

For lesions that are no longer visible following treatment, discuss with Sponsor for continued injection. Distant lesion(s) assessed for "abscopal" response should not be injected, unless approved by the Sponsor Medical Monitor or designee. Deviation from the injectate volumes specified in [Table 3](#) and [Table 4](#) for individual lesions may be permitted upon approval by the Sponsor Medical Monitor or designee.

Table 3 Determination of Intratumoral MK-1454 Injection Volume Per Lesion Based on Lesion Size

Lesion Size (longest dimension)	Injection Volume
>5 cm	3 mL
>2.5 cm to 5 cm	2 mL
≥1.0 cm to 2.5 cm	1 mL

Table 4 Determination of Intratumoral MK-1454 Total Injectate Volume Based on Number of Lesions Injected Per Treatment Visit

Deliverable Volume		1 mL	2 mL	3 mL
Number of Lesions	1	1 × 1 mL	1 × 2 mL	1 × 3 mL
	2	NA	2 × 1 mL	1 × 1 mL + 1 × 2 mL
	3	NA	NA	3 × 1 mL
NA not applicable.				

Details on dose calculation, preparation, and administration of MK-1454 are provided in the Procedures Manual.

